4.4.2 Data Collection and Follow-up for Withdrawn Subjects

Withdrawn subjects will have data collected through delivery events. The full data set will include subjects who enroll and receive at least 72 hours of vitamin B₃A dietary supplementation, as the primary outcome will be measured at 72 hours. Every effort will be made to obtain data on all enrolled subjects, even if they are withdrawn and deliver elsewhere.

5 Study Agent

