12.1 FUNDING SOURCE22

12.2 CONFLICT OF INTEREST23

12.3 SUBJECT STIPENDS OR PAYMENTS.....23

13 REFERENCES.....24

List of Abbreviations

ACRONYM	DESCRIPTION
ACOG	American College of Obstetrics and Gynecology
AE	Adverse event
ALT	Alanine aminotransferase
ANOVA	Analysis of variance
APGAR	APGAR score
AST	Aspartate aminotransferase
B ₃ A	B ₃ -amide
BP	Blood pressure
BPP	Biophysical profile
CBC	Complete blood count
CRF	Case report form
CT	Computerized tomography
CTCA v3.0	Common terminology criteria for adverse events v3.0
DSMB	Data Safety and Monitoring Board
EOP	Early onset preeclampsia
EFW	Estimated fetal weight
ET	Endothelin
GI	Gastrointestinal
HELLP	Hemolysis, elevated liver enzymes, low platelets
HIV	Human immunodeficiency virus
INH	Isoniazid
LFTs	Liver function tests (includes AST and ALT)
MRI	Magnetic resonance imaging
MVP	Maximum vertical pocket
MWF	Monday, Wednesday, Friday
NIH	National institutes of health
PHI	Personal health information
NICU	Neonatal intensive care unit
NIH	National institutes of health
NST	Non-stress test
PHI	Protected health information
pK	Pharmacokinetics
PIGF	Placental growth factor
PI	Principal investigator
P/C	Protein to creatinine ratio
RDA	Recommended daily allowance
sFlt-1	Soluble fms-like tyrosine kinase-1
SD	Standard deviation
TID	Three times per day
UA	Umbilical artery
ULN	Upper limit of normal
VEGF	Vascular endothelial growth factor
WHO	World Health Organization

Study Summary

Title	A PHASE II STUDY OF VITAMIN B ₃ AMIDE DIETARY SUPPLEMENTATION IN WOMEN WITH EARLY CONSET PREECLAMPSIA
Short Title	NicPreDose
Protocol Number	001v7
Phase	Phase II
Methodology	Open label
Study Duration	24 months
Study Center(s)	University of North Carolina Women's Clinic/Hospital
Objectives	
 1. To test the effects of a novel oral agent, nicotinamide, on mean arterial pressure (MAP) after 48 hours and 7 days of treatment; 2. To measure safety of nicotinamide in women with early-onset preeclampsia (n=25). Safety defined as development of maternal liver toxicity, defined as $\geq 3x$ ULN of ALT or AST while on treatment, defined as within 24 hours of dose; 3. To determine maternal tolerability of nicotinamide 2.5 gm/day, administered as 1000mg at 8AM and 12MN; 500mg at 4PM 4. To measure pharmacokinetics (pK) of nicotinamide 1000 mg in normal healthy reproductive age women (n=6) and healthy, normotensive pregnant women (n=6).

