
Statistical Methodology
	
Primary Outcome
 
• Mean arterial blood pressure before, 48 hours, and 7 days after daily dosing 
Secondary Outcomes
 
• Maternal liver toxicity: the proportion of women who develop elevated liver function tests (ALT and/or AST \geq 3x ULN within 24 hours of study drug) will be determined and compared to expected proportion of 20%• Maternal side effects (nausea, vomiting, rash, headache)• Optional: Plasma nicotinamide and 2-pyridone levels; sFlt-1 and PIGF levels

1. Introduction

This document is a protocol for a human research study. This study is to be conducted according to US and international standards of Good Clinical Practice (FDA Title 21 part 312 and International Conference on Harmonization guidelines), applicable government regulations and Institutional research policies and procedures.

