- Blood sampling at baseline (pre-dose), 2 hours post dose, 8 hours post dose and 24 hours post dose.
- Urine sample at baseline (pre-dose), 8 hours post dose and 24 hours post dose.
- This will be done either in the clinic or the CTRC

6.3 **Laboratory specimen handling procedures**

Blood for research purposes will be collected at the time of clinically indicated blood draws. Specimens will be labeled with the subject's unique study ID and processed.

Specimens to be tested for circulating sFlt-1 and PlGF levels will be stored and shipped as a single batch on dry ice to the research laboratory at Harvard University. The interassay coefficient of variance for sFlt1 and PlGF immunoassays ranges from 2.6% to 3.0%.

Specimens collected for nicotinamide and 2-pyridone measurements will be sent to the UNC School of Pharmacy Lab ([name]). [name] developed a LC-MS/MS method using protein precipitation (acetonitrile) to measure nicotinamide and 2-pyridone during our previous phase I study.

7 **Statistical Plan**

7.1 **Statistical Methods**

Sample size: The study sample size was calculated to the primary outcome of MAP. We stipulated *a priori* that $\alpha = .05$ and $\beta = 0.2$. Using the highest BP measured within each 24-hr period and applying the following formula we will calculate daily MAP:

$$\text{mean arterial BP} = [2(\text{diastolic BP}) + \text{systolic BP}] \div 3$$

Assuming that the mean (\pm sd) MAP at enrollment of our subjects is 107 (\pm 10) mm Hg, to detect a difference from enrollment to 48 hours after treatment of 7 mm Hg in MAP requires that 20 subjects be enrolled. We will enroll 24 to allow for 20% attrition due to delivery prior to 48 hours of treatment.

- We will use a repeated measurement ANOVA to compare baseline MAP to MAP at 48 hours, 7 days and weekly thereafter until delivery or 34 weeks.
- Maternal liver toxicity: the proportion of women who develop elevated liver function tests (ALT and/or AST \geq 3x ULN within 24 hours of study drug) will be determined and compared to expected proportion of 20%.
- Descriptive report of proportion of women with
 - Side effects
 - Fetal effects

7.2 **Subject Population(s) for Analysis**

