All subjects will be included in the analysis, regardless of whether they received investigational agent. Subject demographic and baseline characteristics will be summarized. Descriptive summaries will include the number of subjects, mean, standard deviation, median, minimum and maximum for continuous parameters, frequency and percentages for categorical parameters.

8 Safety and Adverse Events

The PI and/or study staff will conduct daily medical monitoring for unanticipated problems, AEs, and serious AEs and record and report them to the UNC or WakeMed (respectively-dependent on where they are cared for) IRB and FDA as outlined below (Sections 8.2, 8.3, 8.5). The FDA will be notified after 1 case of liver toxicity and after every 1 case of delivery within 48 hours of enrollment, and will conduct ad-hoc review as they deem appropriate.

Study stopping rules and subject withdrawal for safety reasons are described previously (Section 4.4) and below (Section 8.4).

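### Section 4.4.2 sets the primary outcome at 72 hours and limits the full data set to women with at least 72 hours of drug, against 48 hours, 7 days and all subjects elsewhere in the plan

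*Combined protocol and SAP*

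**What the plan says.** Section 4.4.2, on data collection for withdrawn subjects, contains two linked statements. "The full data set will include subjects who enroll and receive at least 72 hours" of the supplement defines a data set. "as the primary outcome will be measured at 72 hours" gives the reason for it.

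Elsewhere the plan says:

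- **Study Summary, Objectives:** the effect is tested "on mean arterial pressure (MAP) after 48 hours and 7 days of treatment".
- **Study Summary, Statistical Methodology:** the primary outcome is "Mean arterial blood pressure before, 48 hours, and 7 days after daily dosing".
- **Section 3.2:** the primary outcome is the highest MAP in a 24-hour period, with no time point.
- **Section 7.1, sample size:** "to detect a difference from enrollment to 48 hours after treatment of 7 mm Hg in MAP requires that 20 subjects be enrolled", and "We will enroll 24 to allow for 20% attrition due to delivery prior to 48 hours of treatment".
- **Section 7.1, analysis:** a repeated-measures ANOVA will "compare baseline MAP to MAP at 48 hours, 7 days and weekly thereafter until delivery or 34 weeks".
- **Section 7.2:** "All subjects will be included in the analysis, regardless of whether they received investigational agent".

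The early-delivery notices to the FDA (section 8) and the DSMB (section 8.6) also count to 48 hours.

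**The concern.** The plan gives two answers to each of two questions: when the primary outcome is measured, and which women count. The answers cannot both hold. A woman who delivers or stops drug at 60 hours is outside the full data set of 4.4.2 and inside the population of 7.2, and she has passed the 48-hour point on which the study was sized.

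If 4.4.2 were followed, every woman leaving between 48 and 72 hours would be left out of the MAP comparison. The 20% allowance in 7.1 does not cover that loss, because it is defined as delivery before 48 hours.

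The study is open label with one arm and about two dozen women. With two rules in the text, an analyst could select the set and time point after seeing the pressures, and a reader could not tell which result had been pre-specified.

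**Working it through.** **1. The passages compared**

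| Place | Time point for MAP | Who counts |
|---|---|---|
| 4.4.2 | 72 h | at least 72 h of drug |
| Objectives and synopsis outcome | 48 h and 7 days | not stated |
| 3.2 | none given | not stated |
| 7.1 | sized on 48 h; tests 48 h, 7 days, weekly | delivery before 48 h treated as attrition |
| 7.2 | none given | all subjects, treated or not |

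Only 4.4.2 mentions 72 hours, and no 72-hour MAP analysis is described.

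**2. The plan's own sample size**

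Inputs from 7.1: difference 7 mm Hg, SD at enrollment 10, alpha 0.05, power 80%. The SD of the change is not given. It equals 10 × √(2(1 − r)), where r is the correlation between a woman's baseline and 48-hour MAP. With r = 0.5 (assumed) it is 10. A two-sided paired t-test (noncentral t) then needs 19 women, and r = 0.45 gives exactly 20. The stated 20 is reproduced, as a 48-hour calculation.

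For attrition, 20 × 1.2 = 24, the number in 3.1 and 7.1. The division 20 / (1 − 0.2) = 25 matches the 25 preeclamptic women in the synopsis. Both totals are carried below.

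**3. Women remaining at 72 hours**

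The documents give no exit rate between 48 and 72 hours. If the rate implied by 20% lost in two days continues (assumed), the hazard is −ln(0.8)/2 = 0.1116 per day. The share remaining at day 3 is 0.8^1.5 = 0.716, so 28.4% are lost.

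- 24 enrolled: 24 × 0.8 = 19.2 at 48 h; 24 × 0.716 = 17.2 at 72 h.
- 25 enrolled: 25 × 0.8 = 20.0 at 48 h; 25 × 0.716 = 17.9 at 72 h.

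The table varies the exit rate from 48 to 72 hours as a multiple of that hazard. Remaining women = number at 48 h × exp(−multiple × 0.1116), rounded. Power is for 7 mm Hg with SD of change 10.

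| Multiple | From 24: women, power | From 25: women, power |
|---|---|---|
| 0 | 19, 82% | 20, 84% |
| 0.5 | 18, 80% | 19, 82% |
| 1 | 17, 77% | 18, 80% |
| 1.5 | 16, 75% | 17, 77% |

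**4. Sensitivity to the correlation and effect on precision**

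Going from 19 to 17 women takes power from 68% to 63% if r = 0.3 (SD of change 11.8), and from 96% to 94% if r = 0.7 (SD 7.7). With SD 10, the 95% confidence interval half-width is t × 10/√n: 2.101 × 10/√19 = 4.82 mm Hg with 19 women and 2.120 × 10/√17 = 5.14 mm Hg with 17, a difference of 0.3 mm Hg.

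**The case against.** **Section 7.2 governs.** It is the section on analysis populations, whereas the 72-hour sentence sits under data collection and is followed by a commitment to obtain data on every enrolled woman. The full data set might mean only completeness of collection. This has weight, and 7.2 is the likelier governing text. But the sentence sets an exposure threshold and justifies it by the timing of the primary outcome, which is how an analysis rule reads, and no text gives 7.2 precedence. Section 7.1 also counts delivery before 48 hours as attrition, which fits poorly with including all subjects.

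**72 hours may be loose wording for the 48-hour value.** MAP is a 24-hour maximum, and the plan does not say whether the 48-hour value covers hours 24–48 or 48–72. If the latter, the value is complete only at 72 hours. The Day 3 blood sampling in 6.2 is compatible with that. This reading cannot be excluded and is a good reason to state the window. It does not reconcile the text: the attrition allowance stops at 48 hours, and an exposure threshold still contradicts 7.2.

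**The effect is small.** That stands. The unstated correlation moves power far more than the 72-hour rule does.

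A reader might infer that losses must exceed the 20% allowance, or that power must fall below target. Neither follows: with no exits from 48 to 72 hours nothing is lost, and with 25 women and a constant rate power is about 80%. A reader might also infer a biased MAP result. Its size and direction would depend on how leaving relates to pressure, which the documents do not describe. Nor can a flaw in liver-safety monitoring be inferred: no text applies the 72-hour set to liver toxicity or the stopping rules. Section 4.4.1 counts per subjects enrolled, and section 8.4 gives a percentage without stating its denominator.

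**Conclusion.** The conflict is real and lies in operative text: 4.4.2 contradicts the objectives, the synopsis and 7.1 on timing, and 7.2 on who is analysed. It should be fixed because it leaves the pre-specified primary result open, not because the numerical loss is large.

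Under a constant exit rate and an SD of change of 10 mm Hg, following 4.4.2 costs about two women: 19 to 17 if 24 enroll, or 20 to 18 if 25 enroll. Power falls by about 4 to 5 points, to 77% or 80%. Neither assumption comes from the documents, and the loss is zero if nobody leaves in the third day. No claim is made about bias in MAP or about the safety stopping rule.

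**What to change.** - **Section 4.4.2:** delete the 72-hour sentence, or replace it with a reference to 7.2.
- **Section 7.1:** state that the change from baseline to 48 hours, on which the study is sized, is the primary comparison. Keep 7 days as the other stated time point. Say which 24-hour period supplies the 48-hour MAP.
- **Section 7.2:** state that MAP is analysed in all women of the preeclampsia cohort with a baseline MAP, whatever their treatment duration. Use a mixed model on all available MAP values, so that a woman without a 7-day value still counts at 48 hours. Report how many women have no 48-hour MAP, and why.

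The cost is wording in three sections, with no new patients or visits. The downside is that women with short exposure are included and that the mixed model assumes MAP is missing at random, which should be stated with the result.

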5.1 Description

The investigational agent is

Vitamin B₃-amide; 2.5 Gm daily, provided as 500mg oral capsules in three divided doses: administered as 1000mg at 8AM and 12MN; 500mg at 4PM, provided by Major Pharmaceuticals

[name]

Advisor, Contracts and Billing

[name]

[name]

Office: [contact] | [contact]

Email: [contact]

5.2 Treatment Regimen

Subjects will receive vitamin B₃-amide dietary supplementation, 2.5Gm/day daily until delivery or 34 weeks' gestation whichever occurs first. “On-treatment” is defined as 24 hours of study drug.

5.3 Preparation and Administration of Study Agent

Major Pharmaceuticals will supply the vitamin B₃-amide (study agent). The study agent will be stored by either the UNC or the WakeMed pharmacy and dispensed via pharmacy services following enrollment.

5.4 Subject Compliance Monitoring

Medication admission records will be examined by study staff to confirm dispensing of the study agent. Subjects will be queried daily by study staff regarding compliance with study regimen. If the patient goes home on therapy, she will be given a weeks' supply of the study medication and her compliance monitored by study staff.

5.5 Prior and Concomitant Therapy

Subjects will have clinical treatment decisions made by the primary physician, independent of study participation. All subjects will receive standard care as noted below:

- Daily prenatal vitamin
- Blood sampling for hematologic, liver, and kidney function at enrollment and every 2-7

- days thereafter
- Magnesium sulfate for seizure prophylaxis
 - Betamethasone to accelerate fetal lung maturity
 - Antihypertensive agents as needed, determined by primary clinician
 - At least biweekly fetal surveillance by NST (30 minutes of continuous fetal heart rate monitoring) or BPP (30 minutes of ultrasound to monitor for fetal breathing, movement, fluid)
 - Weekly ultrasound to measure amniotic fluid and UA Dopplers

5.6 Receiving, Storage, Dispensing and Return

5.6.1 Receipt of Supplies

Triangle Compounding Pharmacy will ship the vitamin B₃-amide directly to the Pharmacy. Upon receipt, an inventory will be performed and an investigational agent receipt log filled out and signed by the person accepting the shipment. Designated study staff will count and verify that the shipment contains all the items noted in the shipment inventory. Any damaged or unusable study agent in a given shipment will be documented in the study files.

5.6.2 Storage

The study agent will be stored in a cool, well-ventilated area at the Pharmacy. The vitamin B₃-amide should be kept away from heat, sources of ignition, and from incompatibles such as oxidizing agents, moisture. Vitamin B₃-amide is hydroscopic, air and light sensitive and should be stored in light-resistant containers.

5.6.3 Dispensing of Study Agent

The Pharmacy will dispense vitamin B₃-amide. Regular reconciliation will be performed to document study agent assigned, consumed, and remaining. This reconciliation will be logged on the study log.

5.6.4 Return or Destruction of Study Agent

At the completion of the study, there will be a final reconciliation of study agent shipped, consumed, and remaining. This reconciliation will be logged on the reconciliation form, signed and dated. Any discrepancies noted will be investigated, resolved, and documented prior to return or destruction of unused investigational agent. Vitamin B₃-amide destroyed on site will be documented in the study files.

6 Study Procedures

6.1 Eligibility

All study procedures will be conducted in the UNC Women's Clinic or Hospital. Study staff will review records on a daily basis. Eligibility for participation is outlined above. Briefly, women with suspected hypertensive complications of pregnancy at 24-33 3/7 weeks' gestation and no exclusion criteria are eligible. Eligible women will be approached after study staff obtains verbal consent to do so from the primary provider (study staff will confirm with primary provider that the woman is a candidate for expectant management/delayed delivery and there is a viable fetus).

Women who agree to participate will sign written consent and be assigned a unique study ID that will be used to identify all study data collection forms and research specimens. The master

list linking the unique study ID with subject PHI will be kept on a locked computer file in a password protected file.

Healthy women will be recruited from the UNC Women's Clinic at the time of a routine prenatal appointment or well-woman gynecologic visit. Eligible women will be approached after study staff obtains verbal consent to do so from the primary provider. Women who agree to participate will sign written consent and be assigned a unique study ID that will be used to identify all study data collection forms and research specimens. The master list linking the unique study ID with subject PHI will be kept on a locked computer file in a password protected file.

6.2 Study intervention and procedures for participants with early onset severe preeclampsia

The respective pharmacy will dispense vitamin B₃-amide, which will be administered given to the subject by study staff if out-patient or by in-patient nursing staff if in-patient. Study staff will meet with subjects at each prenatal visit or daily [(M-F) if in the hospital] to discuss compliance and side effects.

Clinical care will continue per recommendations of primary obstetrician caring for the patient. Standard procedures may include:

- 24-hr urine collection for protein excretion at admission
- Blood sampling for hematologic, liver, and kidney function at enrollment and every 2-3 days thereafter
- Physical examination by primary clinical provider
- Weight and intake/output measurement as ordered by primary clinical provider
- Magnesium sulfate for seizure prophylaxis
- Betamethasone to accelerate fetal lung maturity
- Antihypertensive agents
- Daily fetal surveillance by NST (30 minutes of continuous fetal heart rate monitoring) or BPP (30 minutes of ultrasound to monitor for fetal breathing, movement, fluid)
- Weekly ultrasound to measure amniotic fluid and UA Dopplers

The primary obstetrician will make decisions regarding indication and timing of delivery. Clinical management of the infant after delivery will be per standard treatment dictated by the neonatologist caring for the baby.

Study procedures include:

- Daily administration of vitamin B₃-amide, 2.5Gm given as administered as 1000mg at 8AM and 12MN; 500mg at 4PM
- Daily (if in-patient) or with each prenatal visit (if out-patient) study nurse visit to query side effects
- Optional blood sampling to coincide with clinical blood draws to measure nicotinamide and 2-pyridone, sFlt-1 and PIGF levels
- Optional blood sampling for Nicotinamide levels at the following times:
 - Day 1 - Baseline – pre 1st dose; Peak – 2 hrs post 1st dose; Trough – pre 2nd dose
 - Day 3 – Trough – pre AM dose; Peak – 2 hrs post AM dose
 - Day 7 - Trough – pre AM dose; Peak – 2 hrs post AM dose
 - Cord blood following delivery.
- Chart abstraction to review maternal liver function testing results, delivery data (up until discharge) and neonatal data (until 30 days of age or until discharge, whichever occurs

first)

6.2a Study intervention and procedures for healthy pregnant and non-pregnant controls

- Administration of a single dose (1000mg) of Nicotinamide at 8AM.
- Blood sampling at baseline (pre-dose), 2 hours post dose, 8 hours post dose and 24 hours post dose.
- Urine sample at baseline (pre-dose), 8 hours post dose and 24 hours post dose.
- This will be done either in the clinic or the CTRC

6.3 **Laboratory specimen handling procedures**

Blood for research purposes will be collected at the time of clinically indicated blood draws. Specimens will be labeled with the subject's unique study ID and processed.

Specimens to be tested for circulating sFlt-1 and PlGF levels will be stored and shipped as a single batch on dry ice to the research laboratory at Harvard University. The interassay coefficient of variance for sFlt1 and PlGF immunoassays ranges from 2.6% to 3.0%.

Specimens collected for nicotinamide and 2-pyridone measurements will be sent to the UNC School of Pharmacy Lab ([name]). [name] developed a LC-MS/MS method using protein precipitation (acetonitrile) to measure nicotinamide and 2-pyridone during our previous phase I study.

7 **Statistical Plan**

7.1 **Statistical Methods**

Sample size: The study sample size was calculated to the primary outcome of MAP. We stipulated *a priori* that $\alpha = .05$ and $\beta = 0.2$. Using the highest BP measured within each 24-hr period and applying the following formula we will calculate daily MAP:

$$\text{mean arterial BP} = [2(\text{diastolic BP}) + \text{systolic BP}] \div 3$$

Assuming that the mean (\pm sd) MAP at enrollment of our subjects is 107 (\pm 10) mm Hg, to detect a difference from enrollment to 48 hours after treatment of 7 mm Hg in MAP requires that 20 subjects be enrolled. We will enroll 24 to allow for 20% attrition due to delivery prior to 48 hours of treatment.

- We will use a repeated measurement ANOVA to compare baseline MAP to MAP at 48 hours, 7 days and weekly thereafter until delivery or 34 weeks.
- Maternal liver toxicity: the proportion of women who develop elevated liver function tests (ALT and/or AST \geq 3x ULN within 24 hours of study drug) will be determined and compared to expected proportion of 20%.
- Descriptive report of proportion of women with
 - Side effects
 - Fetal effects

7.2 **Subject Population(s) for Analysis**

All subjects will be included in the analysis, regardless of whether they received investigational agent. Subject demographic and baseline characteristics will be summarized. Descriptive summaries will include the number of subjects, mean, standard deviation, median, minimum and maximum for continuous parameters, frequency and percentages for categorical parameters.

8 Safety and Adverse Events

The PI and/or study staff will conduct daily medical monitoring for unanticipated problems, AEs, and serious AEs and record and report them to the UNC or WakeMed (respectively-dependent on where they are cared for) IRB and FDA as outlined below (Sections 8.2, 8.3, 8.5). The FDA will be notified after 1 case of liver toxicity and after every 1 case of delivery within 48 hours of enrollment, and will conduct ad-hoc review as they deem appropriate.

Study stopping rules and subject withdrawal for safety reasons are described previously (Section 4.4) and below (Section 8.4).

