Number of Subjects	37 (25 preeclamptic; 6 non-pregnant; 6 healthy, normotensive, pregnant)

Diagnosis and Main Inclusion/Exclusion Criteria
	
Diagnosis and Inclusion Criteria for women with severe preeclampsia
 
• Maternal age 18-45 years• Singleton or twin pregnancy with no known fetal anomalies• Early-onset preeclampsia defined as:
○ Early-onset: between 24 weeks 0 days and -33 weeks 3 days, based on menstrual dating confirmed by first or second trimester ultrasound OR second trimester ultrasound if menstrual dating unavailable;○ Preeclampsia:
▪ New onset hypertension and proteinuria, with systolic BP \geq 140 mm Hg and/or diastolic BP \geq 90 mm Hg on two occasions 6 hours apart and > 300 mg proteinuria on 24 hour urine collection OR urine P/C ratio >0.3;▪ New onset hypertension and NO proteinuria, with systolic BP \geq 140 mm Hg and/or diastolic BP \geq 90 mm Hg on two occasions 6 hours apart and one or more of the following: serum creatinine >1.1 mg/dL or doubling from baseline ,or central nervous system symptoms or visual changes▪ Severe gestational hypertension defined as new onset systolic BP \geq 160 mm Hg and/or diastolic BP \geq 105.○ Candidate for expectant management for at least 48 hours○ Deemed clinically stable by primary clinician and candidate for expectant management (delayed delivery) for at least 48 hours;• Maternal liver function tests < 2x ULN• Maternal platelet count \geq 100,000 mm³• Planned expectant management• Pre-existing medical diseases such as hypertension, diabetes, endocrine disorders, gastrointestinal diseases, are well controlled• Fetal well-being established by estimated fetal weight \geq 5th %tile; normal amniotic fluid volume (MVP \geq 2 cm); normal UA Dopplers; or reactive NST or BPP > 6• Delivery not anticipated within 48 hours of enrollment 
Exclusion Criteria for women with severe preeclampsia
 
• Pre-existing renal disease (creatinine \geq 1.5 mg/dL)• Any pre-existing medical condition that would increase risk for liver toxicity (e.g. hepatitis B or C; HIV; INH use)• Eclampsia; cerebral edema on CT/MRI; headache unrelieved by analgesics• Evidence of liver dysfunction (LFTs \geq 2x ULN)• Thrombocytopenia (platelets < 100,000 mm³)• Pulmonary edema• HELLP syndrome• Evidence of fetal compromise: EFW < 5th percentile; or BPP < 6; or absent or reverse diastolic UA blood flow; or oligohydramnios (MVP < 2 cm)

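### Section 7.1's enrolment of 24 leaves 19.2 women, not the required 20, after its own 20% attrition; the Study Summary's 25 is the consistent figure, and primary time points and analysis set also differ between sections

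*Combined protocol and SAP*

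**What the plan says.** **Sample size.** Section 7.1 sets alpha at 0.05 and beta at 0.2. It assumes that "MAP at enrollment of our subjects is 107" mm Hg with an SD of 10, and says that "to detect a difference from enrollment to 48 hours after treatment of 7 mm Hg in MAP requires that 20 subjects be enrolled". It continues: "We will enroll 24 to allow for 20% attrition due to delivery prior to 48 hours of treatment". Section 3.1 also gives 24 women with early-onset preeclampsia, plus 12 healthy controls. The Study Summary gives 25 in two places: Objective 2 ("To measure safety of nicotinamide in women with early-onset preeclampsia (n=25") and the Number of Subjects row ("37 (25 preeclamptic; 6 non-pregnant; 6 healthy, normotensive, pregnant").

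**Primary time points.** The first objective in the Study Summary concerns the effect "on mean arterial pressure (MAP) after 48 hours and 7 days of treatment", and its primary outcome is "Mean arterial blood pressure before, 48 hours, and 7 days after daily dosing". Section 7.1 plans a repeated-measures ANOVA to "compare baseline MAP to MAP at 48 hours, 7 days and weekly thereafter until delivery or 34 weeks". Section 4.4.2 instead puts the primary outcome at 72 hours.

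**Analysis set.** Section 4.4.2 restricts the full data set to women who had 72 hours or more of supplementation. Section 7.2 analyses every subject, including any who never took the agent.

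**The concern.** Three things do not fit together.

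- The inflation for attrition multiplies by 1.20 where it should divide by 0.80. The enrolment figure therefore does not deliver the number that the same paragraph says is needed.
- The protocol carries two enrolment targets. It is unclear whether enrolment is complete at 24 or 25 women, or at 36 or 37 participants in all.
- The primary outcome falls at 48 hours and 7 days in some sections and at 72 hours in another, and the two descriptions of the analysis set differ. A woman who delivers at 60 hours is in the analysis under 7.2 and outside the full data set under 4.4.2. If this stays open, the choice could be made after the data are seen.

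There is also a smaller reporting gap. The comparison is within each woman, so its power depends on the SD of the 48-hour change. Section 7.1 gives only the SD of MAP at enrolment and does not say whether the test is one- or two-sided.

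**Working it through.** **Inputs from the documents.** Section 7.1: alpha 0.05, power 0.80, difference 7 mm Hg, SD of MAP at enrolment 10, 20 women required, 20% attrition, 24 enrolled. Section 3.1: 24 women and 12 controls. Study Summary: 25 women, 37 in total.

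**Assumptions made here.** The SD of the change is 10 and the test is a two-sided paired t-test (noncentral t). Section 7.1 states neither. It plans a repeated-measures ANOVA, so the power figures are approximations.

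**1. Reproducing the required 20.** With a standardised change of 7/10 = 0.7:

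| Women at 48 h | Power |
|---|---|
| 18 | 79.9% |
| 19 | 82.3% |
| 20 | 84.4% |

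The smallest n reaching 80% is 19, so the plan's 20 is reproduced to within one woman.

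**2. Reproducing the 24.** 20 x 1.20 = 24, which is exactly the plan's figure.

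**3. Applying the stated attrition.**
- Retained from 24: 24 x 0.80 = 19.2, below 20.
- Loss that 24 can absorb while keeping 20: (24 - 20)/24 = 16.7%.
- Enrolment needed: 20/(1 - 0.20) = 25. Check: 25 x 0.80 = 20.0.

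**4. Totals.** 24 + 12 = 36 under 3.1 and 7.1; 25 + 12 = 37 under the Study Summary.

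**5. Effect on power.** Let the number retained be binomial with probability 0.8 and average the paired-t power over it. This gives 82.2% with 24 enrolled and 83.9% with 25, a difference of 1.7 percentage points.

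**6. What the 80% depends on.** The largest SD of the 48-hour change at which power is still 80%:

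| Women at 48 h | Two-sided test | One-sided test |
|---|---|---|
| 20 | about 10.6 | about 12.1 |
| 19 | about 10.3 | about 11.8 |

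**7. Time points and analysis set, side by side.**

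| Place | Primary time point(s) | Women included |
|---|---|---|
| Study Summary | 48 hours and 7 days | not stated |
| 7.1, sample size | 48 hours | attrition from delivery before 48 hours |
| 7.1, analysis | 48 hours, 7 days, then weekly | not stated |
| 4.4.2 | 72 hours | at least 72 hours of supplementation |
| 7.2 | not stated | all subjects |

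The attrition allowance matches the 48-hour time point. It does not cover 7 days, and no other allowance is given for 7 days.

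**The case against.** The best defence is that nothing of substance is lost. The shortfall is about one woman. If the SD of the change is 10 and the test is two-sided, 19 women are enough for 80% power, the expected 19.2 meets that, and average power with 24 enrolled exceeds 80%. So 24 misses the stated 20 but not the power target. Under the same assumptions the chance of keeping at least 19 women is 66% with 24 enrolled and 78% with 25. All of this stands, and it limits the point to correctness and consistency.

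The defence also applies to the SD. An SD of 10 at each time with a correlation of 0.5 gives an SD of change of 10 x sqrt(2 x (1 - 0.5)) = 10, so the plan's figure may be sound. The documents do not show that it is wrong, only that the assumption is unstated.

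Two stronger readings are tempting and are not supported.

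- *The trial is underpowered.* The calculation does not show this, and without the SD of the change the direction of any error is unknown.
- *Section 1.1's delivery rates by sFlt-1/PlGF ratio forecast how many women remain at 7 days.* The trial's mix of ratios is not given, and the trial selects stable women not expected to deliver within 48 hours. The lower of the two one-week rates, 10%, is also below the 20% that 7.1 expects to deliver before 48 hours, so it would leave more women at 7 days than at 48 hours. What can be said is that 7.1 makes no allowance for 7 days.

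The timing and analysis-set conflicts are separate from the arithmetic and do not make the one-woman discrepancy any larger. They are still contradictions in the current text.

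**Conclusion.** The point holds in a limited form. That 24 does not allow for 20% attrition from a required 20, and that 25 does, follows from the plan's own figures with no outside assumption. So does the conflict between 24 and 25 women (36 and 37 in total). The consequence for power is small: 82.2% against 83.9%, given an SD of change of 10, a two-sided paired t-test and binomial loss at 20%.

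The conflict between 4.4.2 and the Study Summary, 7.1 and 7.2 is read directly from the text and leaves the primary time points and analysis set undefined. The missing SD of the change and sidedness are a minor reporting gap, because the required 20 is approximately reproduced. The correction should be made mainly so that the protocol carries one enrolment number, one set of primary time points and one analysis set.

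**What to change.** - **Enrolment.** State 25 in sections 3.1 and 7.1 to match the Study Summary (25 x 0.8 = 20; 37 in total). Alternatively, keep 24 throughout, change the Study Summary to 24 and 36, and state in 7.1 that about 19 women are expected at 48 hours.
- **Time points and analysis set.** Reconcile 4.4.2 with the 48-hour and 7-day primary outcome and with 7.2, so that one set of primary time points and one analysis set apply. Say in 7.1 that the attrition allowance refers to 48 hours, and state what is expected at 7 days.
- **Power statement.** Give the SD of the 48-hour change that was assumed, its source if there is one, and the sidedness of the test. Describe the 80% as conditional on these. If the SD that the sponsor can support exceeds the limit in step 6 of the working for the chosen sidedness and number of women, restate the power.

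**Cost.** These are text changes, with no enrolment beyond the 25 already in the Study Summary. Under section 11 they go to the IRB as an amendment. A sourced SD of the change needs data that the documents do not contain; without such data it can be given as an assumption.
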